Grade 3 : QTcF > 500msec as identified on the ECG by the investigator	
Hold infigratinib.
 
 
Monitor patient with hourly ECGs until the QTcF has returned to baseline.
 
Perform further monitoring as clinically indicated.
 
Exclude other causes of QTcF prolongation such as hypokalemia, hypomagnesaemia and decreased blood oxygenation.
 
Patients should receive appropriate electrolyte replacement and should not receive further infigratinib until electrolytes are documented to be within normal limits.
 
 
Once the QTcF prolongation has resolved and if the QTcF prolongation was confirmed by the central reader, patients may be re-treated at one lower dose level at the investigator's discretion
 
 
ECG assessments should be performed for 2 additional cycles at the same frequency as in cycle 1 or as clinically indicated 
 
If ECG assessments show no QTcF <math>\geq</math> 481 msec, for subsequent cycles ECG monitoring will be performed as per visit schedule.
 
If ECG assessments are still abnormal (QTcF <math>\geq</math> 481 msec and <math>\leq</math> 500 msec), then ECG monitoring must continue at the same frequency as in cycle 1 or as clinically indicated, for all subsequent cycles
 
 
 
Patients who experience recurrent QTcF <math>\geq</math> 500msec after one dose reduction will be discontinued from study.
 
 
NB: If ventricular arrhythmia or Torsades de Pointes is observed in a patient, he/she will be discontinued from the study.

Cardiac disorders - others Grade $\geq$ 3, or congestive heart failure $\geq$ 2	Discontinue patient from study treatment.
Investigations-Hematology	

A Phase 0 Study of Infigratinib in Recurrent Glioblastoma Patients  
 Protocol 2020-08

Worst Toxicity CTCAE v5.0 Grade (unless otherwise specified)	Recommended Dose Modifications any time during a cycle of therapy
ANC decreased (Neutropenia) Grade 3 (ANC < 1.0 - 0.5 x 10  /L)	Hold dose of infigratinib until resolved to CTCAE Grade ≤ 1 or baseline, then 
 
• If resolved in ≤ 7 days, maintain dose level of infigratinib
 
• If resolved in > 7 days, ↓ 1 dose level of infigratinib.
 

Grade 4 (ANC < 0.5 x 10  /L)	Hold dose of infigratinib until resolved to CTCAE ≤ Grade 1, ↓ 1 dose level of infigratinib.

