Asymptomatic amylase and/or lipase elevation Grade 3 ( $> 2.0 - 5.0 \times \text{ULN}$ )	
 
• Hold dose of infigratinib until resolved to CTCAE Grade <math>\leq 2</math>.
 
• <math>\downarrow 1</math> dose level of infigratinib
 
 
Note: A CT scan or other imaging study to assess the pancreas, liver, and gallbladder must be performed within 1 week of the first occurrence of any CTCAE <math>\geq</math> Grade 3 amylase and/or lipase.
 
If asymptomatic CTCAE Grade 2 elevations of lipase and/or amylase occur again at the reduced dose, patients will be discontinued permanently from study treatment.

Grade 4 ( $> 5.0 \times \text{ULN}$ )	Discontinue patient from study treatment
Hyperphosphatemia Serum phosphorus $> 5.5 - 7.0 \text{ mg/dL}$	See Table 4 Maintain dose level of infigratinib, but modify phosphate lowering therapy

A Phase 0 Study of Infigratinib in Recurrent Glioblastoma Patients

Protocol 2020-08

Worst Toxicity CTCAE v5.0 Grade (unless otherwise specified)	Recommended Dose Modifications any time during a cycle of therapy
Serum phosphorus >7.0 – 10.0 mg/dL despite phosphate lowering therapy	
Hold infigratinib dose until resolved to serum phosphorus <math>\leq</math> 5.5 mg/dL
 
 
if resolved by <math>\leq</math> 14 days after suspending infigratinib, <math>\downarrow</math> 1 dose level
 
if does not resolve within 14 days of suspending infigratinib, discontinue patient from the study.
 

Serum Pi $>$ 10.0 mg/dL	Discontinue patient from study treatment
Hypercalcemia Serum calcium grade 2	Hold infigratinib dose until resolved to grade 1 or baseline: 
 
if resolved <math>\leq</math> 7 days after suspending infigratinib, maintain dose level
 
if resolved <math>></math> 7 days after suspending infigratinib, <math>\downarrow</math> 1 dose level
 

Serum calcium $\geq$ grade 3	Discontinue patient from the study
Nervous system disorders	
Neurotoxicity Grade 2	Omit dose of infigratinib until resolved to CTCAE Grade $\leq$ 1, then $\downarrow$ 1 dose level of infigratinib
Grade $\geq$ 3	Discontinue patient from study drug treatment
GI disorders	
Pancreatitis Grade $\geq$ 2	Discontinue patient from study drug treatment

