Diarrhea Grade 1	Maintain dose level of infigratinib, but initiate anti-diarrheal treatment  Note: Antidiarrheal medication is recommended at the first sign of abdominal cramping, loose stools or overt diarrhea. See 6.4.1.3.1

A Phase 0 Study of Infigratinib in Recurrent Glioblastoma Patients  
 Protocol 2020-08

Worst Toxicity CTCAE v5.0 Grade (unless otherwise specified)	Recommended Dose Modifications any time during a cycle of therapy
Grade 2	
Hold dose of infigratinib until resolved to CTCAE Grade <math>\leq 1</math>
 
 
Optimize anti-diarrheal treatment, maintain dose level of infigratinib.
 
For reoccurrence of diarrhea CTCAE Grade 2, hold dose of infigratinib until resolved to CTCAE Grade <math>\leq 1</math>, <math>\downarrow</math> infigratinib by 1 dose level
 

Grade 3	
 
Hold dose of infigratinib until resolved to CTCAE Grade <math>\leq 1</math>
 
Optimize anti-diarrheal treatment
 
<math>\downarrow</math> infigratinib by 1 dose level
 
For reoccurrence of diarrhea CTCAE Grade 3, despite optimal anti-diarrheal treatment, discontinue patient from study treatment.
 

Grade 4	Discontinue patient from study treatment.
Vomiting Grade 2 not controlled by optimal anti-emetic therapy	Hold infigratinib doses until $\leq$ grade 1, $\downarrow$ 1 dose level
Grade 3 not controlled by optimal anti-emetic therapy or Grade 4	Discontinue patient from study
Eye Disorders (confirmed by ophthalmologic examination)	
Retinal disorders Grade 2 CSR and CSR-like events	Hold infigratinib until resolved to $\leq$ grade 1 but refer the patient to a retinal specialist for evaluation 
 
If resolved in <math>\leq 14</math> days, <math>\downarrow</math> infigratinib by 1 dose level
 
If resolved in <math>> 14</math> days, discontinue infigratinib
 

Grade 3 CSR and CSR-like events and any other grade 3 eye disorders	Hold infigratinib until resolved to grade $\leq 1$ . 
 
If resolved in <math>\leq 14</math> days, <math>\downarrow</math> infigratinib by 1 dose level
 
If resolved in <math>> 14</math> days, discontinue infigratinib
 

$\geq$ grade 1 retinal vein occlusion, grade 4 CSR and CSR-like events, and grade 4 other eye disorders	Discontinue infigratinib

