**Table 4 Toxicity Follow-up Evaluation**

Toxicity	Follow-Up Evaluation
Metabolic (hyperphosphatemia)	
Serum phosphorus lowering therapy consisting of dietary phosphate intake restriction and oral phosphate binders should be applied as follows:
 
Calcium-containing phosphate binders are not recommended.
 
Starting Cycle 1 Day 1 (beginning with the midday or evening meal on C1D1):
 
 
• Restriction of dietary phosphate intake to 600 – 800 mg/day, if BMI ≥ 21kg/m^2.
 
• Sevelamer 1 tablet (800mg) per meal; i.e. 3 x 800 mg/day.
 

A Phase 0 Study of Infigratinib in Recurrent Glioblastoma Patients

Protocol 2020-08

	
If serum Pi > 5.5 – 7.0mg/dL:
 
 
• Increase the dose of sevelamer up to 1200mg tid with meals
 
 
If serum Pi > 7.0mg – 9.0mg/dL
 
 
• Increase the dose of sevelamer up to 1600mg (2 tablets per meal) tid with meals
 
 
If serum phosphorus increases > 7.0mg/dL despite phosphorus lowering therapy given for at least 14 days, the infigratinib dose should be held and then dose subsequently reduced. All patients will continue to be followed until resolution to serum phosphorus ≤ 5.5 mg/dL or baseline or stabilization.

Renal	
If serum creatinine CTCAE Grade ≥ 1 has been demonstrated in conjunction with hyperphosphatemia, this parameter must be repeated at least weekly until resolution. 24-hour urine collection should also be obtained for total phosphate, calcium, protein and creatinine clearance within weekly intervals. Ultrasound examination of the kidneys should be performed as indicated to evaluate de-novo calcifications until resolution or stabilization of creatinine.

As a general approach, based on the risk/benefit balance assessment per the investigator: for a participant who experiences a new episode of Grade 3 hematological toxicity after more than 8 weeks following the last episode of same Grade 3 hematological toxicity, the investigator may consider resuming the participant on the same drug dose if the participant satisfies the following conditions:

- The participant showed stable hematological counts (≤Grade 2) during that time frame
- In the absence of any infectious sign or risk factor
- The participant is getting benefit from study treatment.

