## 7 STUDY INTERVENTION DISCONTINUATION AND PARTICIPANT DISCONTINUATION / WITHDRAWAL

### 7.1 DISCONTINUATION OF STUDY INTERVENTION

Discontinuation from treatment does not mean discontinuation from the study, and remaining study procedures should be completed as indicated by the study protocol. If a clinically significant finding is identified (including, but not limited to changes from baseline) after enrollment, the investigator or qualified designee will determine if any change in participant management is needed. Any new clinically relevant finding will be reported as an adverse event (AE).

The data to be collected at the time of study intervention discontinuation will include the end-of-study (EOS) procedures as shown in Section 1.2.

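### No MRI or RANO reading is required after infigratinib is stopped without progression, so 6-month status for the Expansion Cohort's primary endpoint can be lost

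*Combined protocol and SAP*

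**What the plan says.** **Endpoint and analysis.** PFS6, counted from surgery, is the Expansion Cohort's primary endpoint (sections 1.1 and 3). Under 9.4.1 the events are progression and death from any cause, and removal from treatment for symptomatic deterioration also counts as progression. Anyone alive without progression is censored at the last tumor assessment. Section 9.4.5 rules out imputing missing efficacy data. The Efficacy dataset in 9.3 takes in every PK-positive participant with at least one day of Expansion treatment. Section 8.1.4 is narrower: for Expansion RANO, a participant is evaluable only after one full cycle and an MRI in the Expansion Phase.

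**Imaging.** In the Schedule of Activities (1.2), MRI and RANO run every 3 months in Expansion and finish with the entry Last, the visit label of the End of Study Treatment column. Footnote 9 makes MRI routine care. Later contact is a safety call about 30 days after the last dose, then a letter or call about every 3 months for survival (1.1, 4.1.2).

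**Stopping drug.** Section 7.1 gives the general rule: "Discontinuation from treatment does not mean discontinuation from the study, and remaining study procedures should be completed as indicated by the study protocol". Five actions in Table 3 are worded differently:
- recurrent QTcF prolongation: "500msec after one dose reduction will be discontinued from study"
- arrhythmia: "If ventricular arrhythmia or Torsades de Pointes is observed in a patient, he/she will be discontinued from the study"
- phosphorus above 7.0 and up to 10.0 mg/dL: "if does not resolve within 14 days of suspending infigratinib, discontinue patient from the study"
- calcium Grade 3 or higher: "discontinue patient from the study"
- uncontrolled Grade 3, or any Grade 4, vomiting: "discontinue patient from study"

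The more severe phosphorus row, above 10.0 mg/dL, says "Discontinue patient from study treatment".

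**The concern.** The protocol expects some participants to stop drug for reasons other than tumor growth. Table 3 has many mandatory stops, a limit of two dose reductions, and a stop after a dose delay of more than 14 days. A participant who stops this way at, say, month 2 and stays well has a PFS6 status that only a later tumor assessment can settle, and none is required. The gap arises in the Schedule of Activities, whichever way the Table 3 wording is read.

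The primary Expansion result would then rest on censored follow-up in a very small group. Stopping for toxicity may be related to outcome, so the censoring may be informative. The uncertainty from unknown status would also not show in an ordinary confidence interval.

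**Working it through.** **1. Cohort size, reproducing the plan (9.2).** 400 operated per year × 5% = 20 eligible per year; × 50% capture = 10 per year; × 2 years = 20 enrolled, as stated. Expansion share: 20 × 50% = 10.

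**2. Who is affected.**

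| Participant stops drug before 6 months and… | PFS status under the plan |
|---|---|
| progresses by RANO | event (9.4.1) |
| is removed for symptomatic deterioration | event (9.4.1) |
| fails to return because of death or deterioration | event (8.1.4.1) |
| dies later from any cause | event (9.4.1), found through survival follow-up |
| is alive and progression-free, with a later recorded scan | assessed at that scan |
| is alive and stable, with no later recorded scan | censored at the last assessment; 6-month status unknown |

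Only the last row is the problem.

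**3. Size per participant.** With u unknown statuses among n, the undetermined part of the rate is u/n.
- n = 10: u = 1, 2, 3 gives 10, 20, 30 points.
- If Expansion n is 5 or 15 (25% or 75% of 20, assumed), one unknown is 1/5 = 20 points or 1/15 = 6.7 points.

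**4. Illustration (all counts assumed).** Of 10 participants, 4 progress by month 3; 2 then stop drug and are censored; 2 of the remaining 4 progress by month 6.
- Kaplan-Meier PFS6 = (6/10) × (2/4) = 30%.
- If both censored participants in fact progressed: 2/10 = 20%. If neither did: 4/10 = 40%.
- For scale, the exact 80% interval for 3/10 is 11.6% to 55.2%, a width of 43.6 points. The 20 undetermined points are 20/43.6 = 0.46 of that width.

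The documents name Kaplan-Meier for OS (9.4.6), not for PFS6, so the 30% is illustrative. The 20% to 40% bounds do not depend on it.

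**5. Direction (assumed values).** Suppose 20% stop at month 2 while progression-free, and those who stay on drug have PFS6 of 20% with constant hazard. The large-sample Kaplan-Meier value is (0.8 × 0.2^(1/3) + 0.2) × 0.2^(2/3) = 22.8%. If 5% of those who stopped are progression-free at 6 months, the true rate is 0.8 × 0.20 + 0.2 × 0.05 = 17.0%. If 40% are, it is 0.8 × 0.20 + 0.2 × 0.40 = 24.0%. The bias can go either way.

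**6. Denominator.** A participant who stops during Cycle 1 is in the 9.3 Efficacy dataset but not evaluable under 8.1.4. The plan does not say which rule governs PFS6, so even n is open for early stops.

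**7. Length of follow-up needed.** 6 × 30.4375 days (the 9.4.5 conversion) = 182.6, so 183 days from surgery.

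**The case against.** The best defense is that early censoring is likely here but not forced. MRI is routine care, so later scans will probably exist. The censoring rule in 9.4.1 refers to the last assessment without limiting it to time on drug. Section 7.1 asks for remaining procedures to be completed. This stands as far as it goes, but 7.1 reaches only procedures that the protocol indicates, and it indicates no scan after the end-of-treatment visit. Nothing requires a later routine scan to be collected or read by RANO. Routine care makes the repair cheap without making it unnecessary.

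It is also fair to say that the trial is exploratory, has no PFS6 target, and tests no hypothesis on PFS6 (9.1). Two unknowns span less than half of one 80% interval, and the counts used above are assumed. All of that stands. It limits the size of the point and confines it to estimation.

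A further objection is that scans alone are not enough. RANO needs clinical status and corticosteroid dose. A participant off drug may also start another anticancer therapy, for which the plan has no PFS rule, so PFS6 could be credited to that therapy. Both are right, and the remedy has to cover them.

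**Conclusion.** The gap is real but narrow. It concerns an Expansion participant who stops infigratinib before 6 months from surgery without progression or symptomatic deterioration, is alive, and has no later recorded scan. At n of about 10, each such participant leaves about 10 points of a descriptive PFS6 rate undetermined. The number affected is not in the documents; 1 to 3 is an assumption. The reading of the schedule relies on Last being the visit label of the End of Study Treatment column, since the table was extracted by program.

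Three stronger readings are tempting, and the documents do not support them.
- *Every early stop is censored.* Progression, symptomatic deterioration and death all count as events.
- *Table 3 removes five groups from the study and its data.* The wording looks like shorthand. Section 7.1 states the general rule, all participants are followed for survival (1.1 and the End of Study Definition), and nobody leaves the 9.3 datasets. For phosphorus, Table 4 adds "All patients will continue to be followed until resolution to serum phosphorus ≤ 5.5 mg/dL or baseline or stabilization".
- *The adverse event window is badly open.* Section 8.3.4 counts from an undefined last day of participation. Literal extremes would close non-serious recording 7 days after the last dose or at about day 1,833 (5 × 365.25 + 7). But the End of Study Definition ties completion to the phone follow-up, and survival follow-up begins only after the Day 30 call. Open events are followed to resolution or stabilization in any case.

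**What to change.** In 7.1 and the Schedule of Activities:
1. State that participants who stop drug without progression continue to have routine-care MRI about every 3 months collected and read by RANO, with clinical status and corticosteroid dose. This runs until progression, death or at least 183 days from surgery, unless consent is withdrawn.
2. Record the start date of any new anticancer therapy, and state in 9.4.1 how PFS6 handles it.
3. State that the evaluability rule in 8.1.4 does not remove participants from the 9.3 Efficacy dataset for PFS6.

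Editorial only: change the five Table 3 actions to say study treatment, and anchor the 8.3.4 recording windows to the last dose. No decision to stop drug changes.

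Cost: one amendment and one schedule entry. An affected participant needs at most about two extra scans recorded (around months 3 and 6, if the 3-month clock runs from about surgery), with brief clinical data. For 1 to 3 participants that is 1 to 6 scans in total.

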A Phase 0 Study of Infigratinib in Recurrent Glioblastoma Patients  
Protocol 2020-08

Worst Toxicity CTCAE v5.0 Grade (unless otherwise specified)	Recommended Dose Modifications any time during a cycle of therapy
Other ocular/visual toxicity	
≥ grade 3	Hold infigratinib until resolution to ≤ grade 1 If resolution in ≤14 days, ↓ 1 dose level, otherwise discontinue infigratinib
General disorders	
Fatigue Grade 3	Hold dose of infigratinib until resolved to CTCAE Grade ≤ 1 
 
• If resolved in ≤ 7 days, maintain dose level of infigratinib.
 
• If resolved in > 7 days, discontinue patient from study treatment.
 

Other clinically significant AEs	
Grade 3	Hold dose of infigratinib until resolved to CTCAE Grade ≤ 1, then ↓ 1 dose level of infigratinib.
Grade 4	Discontinue patient from study treatment

All dose modifications should be based on the worst preceding toxicity. Once a dose has been reduced it will not be increased at a later time even if there is no toxicity. Patients who require more than two dose reductions of infigratinib will be discontinued from study drug treatment.
 
If a patient requires a dose delay of > 14 days from the intended day of the next scheduled dose of infigratinib then study treatment must be stopped.
	

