#### **6.4.1.3.5 SUPPORTIVE MANAGEMENT RECOMMENDATIONS FOR OCULAR DISORDER**

---

Infigratinib very commonly causes dry eye and blurred vision; other commonly reported ocular events include conjunctivitis, increased lacrimation, punctate keratitis, and visual impairments. CSC/RPED have also been reported. Subjects should receive dry eye prophylaxis with ocular demulcents as needed.

Ophthalmological examinations (performed by an ophthalmologist) should be done at baseline/screening, phase 0 follow-up, every 3-4 months thereafter, and at any time as per physician discretion for visual symptoms. Withhold infigratinib if central serous chorioretinopathy (CSC)/ retinal pigment epithelial detachment (RPED) occurs and permanently discontinue if it does not resolve after 14 days or if it is Grade 4 in severity. Also discontinue infigratinib for other Grade 4 ocular disorders and for Grade  $\geq 1$  retinal vein occlusion. ([QED 2019](#))

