#### 8.2.5 OPHTHALMIC EXAMINATION

Ophthalmic examination will be assessed as per the assessment schedule (Section 1.2) and with any new onset of visual disturbance by an ophthalmologist and should include: visual acuity testing (including corrected distance acuity), slit lamp examination of the anterior eye segment, intraocular pressure (IOP), retinal OCT and dilated fundoscopy. Additional examinations such as specular microscopy and corneal pachymetry will be performed as clinically indicated. In addition, ophthalmic exams should be done as clinically indicated.

---

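### Table 3's Other ocular/visual toxicity row allows re-treatment after a Grade 4 eye event that two other provisions say should end treatment

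*Combined protocol and SAP*

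**What the plan says.** Three provisions govern a severe eye event that is not retinal.

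- **Table 3, Other ocular/visual toxicity.** The grade label is Grade 3 or higher, with no ceiling and no separate Grade 4 line. The action is "Hold infigratinib until resolution to ≤ grade 1 If resolution in ≤14 days, ↓ 1 dose level, otherwise discontinue infigratinib".
- **Table 3, Eye Disorders block**, headed "Eye Disorders (confirmed by ophthalmologic examination". A Grade 3 row covers "Grade 3 CSR and CSR-like events and any other grade 3 eye disorders": hold, reduce one level if resolved within 14 days, otherwise stop. The row below it covers retinal vein occlusion together with "grade 4 CSR and CSR-like events, and grade 4 other eye disorders". Its action is to discontinue, with no recovery window.
- **Section 6.4.1.3.5.** "Also discontinue infigratinib for other Grade 4 ocular disorders". This also has no recovery window. For central serous chorioretinopathy and retinal pigment epithelial detachment, the same section says to "permanently discontinue if it does not resolve after 14 days or if it is Grade 4 in severity".

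The Table 3 footer adds: "All dose modifications should be based on the worst preceding toxicity". Section 8.2.5 requires an ophthalmic examination on schedule and also "with any new onset of visual disturbance by an ophthalmologist".

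**The concern.** A Grade 4 event satisfies the Grade 3-or-higher label. The other ocular/visual row therefore gives a site a clear instruction to resume at a lower dose once the event has settled, where the two other provisions say to stop. The protocol sets no order of precedence among them.

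The stake is participant safety. Followed as written, the row re-exposes someone whom two other provisions take off drug. Eye toxicity is a known effect of this agent: Section 6.4.1.3.5 describes dry eye and blurred vision as very common and lists punctate keratitis and visual impairments among other reported events. A site may also not notice the problem. It could consult that row alone, find a complete instruction and have no reason to raise a query.

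**Working it through.** No sample size or test statistic is involved. The check compares the action each provision gives for the same event.

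**Step 1: grade by recovery time, non-retinal eye event**

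| Grade | Recovery to Grade 1 or lower | Other ocular/visual row | Eye Disorders block | Section 6.4.1.3.5 | Agree? |
|---|---|---|---|---|---|
| 3 | 14 days or less | reduce one level | reduce one level | no rule for non-retinal Grade 3 | yes |
| 3 | more than 14 days | discontinue | discontinue | no rule for non-retinal Grade 3 | yes |
| 4 | more than 14 days | discontinue | discontinue | discontinue | yes |
| 4 | 14 days or less | **reduce one level** | **discontinue** | **discontinue** | **no** |

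The instructions conflict in 1 of 4 combinations.

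**Step 2: does recovery release the event from the Grade 4 rule?** No. The footer ties modifications to the worst preceding toxicity, so the event is still handled as Grade 4 after it has improved. The footer fixes the grade but does not choose between rows. For chorioretinopathy and epithelial detachment, Section 6.4.1.3.5 also treats Grade 4 and failure to resolve by 14 days as separate reasons to stop. Quick recovery is therefore not treated there as cancelling a Grade 4 event.

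**Step 3: does another part of Table 3 settle it?** No. The catch-all row for other clinically significant events says to discontinue at Grade 4, but it is general and the ocular row is specific. Nor can a site dismiss resumption after Grade 4 as an obvious slip, because Table 3 expressly allows it for neutropenia, hemoglobin and platelets.

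**Step 4: dose levels at which it matters (Table 5)**

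- At 125 mg, re-treatment would be at 100 mg: 100/125 = 80% of the starting dose.
- At 100 mg, re-treatment would be at 75 mg: 75/125 = 60% of the starting dose.
- At 75 mg, a further reduction already means discontinuation, unless the investigator discusses going lower with the Safety Officer.

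The conflict arises at 2 of 3 levels.

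**Step 5: participants exposed.** Section 6.1.3 allows no dose modifications in Phase 0, so only the Expansion Cohort is concerned. With 20 Phase 0 participants (Section 9.1) and an estimated 50% going on (Section 9.2), this is 20 × 0.50 = 10. The documents give neither a rate of Grade 4 non-retinal eye events nor a rate of recovery within 14 days, so no expected number of conflicts can be calculated.

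**The case against.** The best defense is that the other ocular/visual row is residual. The block above it deals with confirmed eye disorders and already sends Grade 4 to discontinuation. The later row would then cover what is left, such as a visual symptom that is examined but not confirmed as an eye disorder, which is plausible in patients with brain tumors. On that reading a confirmed Grade 4 eye disorder has only one rule.

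This does not remove the conflict. The row's own heading includes ocular events, and nothing in it limits it to unconfirmed ones. Section 6.4.1.3.5 has no confirmation condition and counts visual impairments among ocular events. Since Section 8.2.5 has an ophthalmologist examine any new visual disturbance, a Grade 4 event would ordinarily be examined, though examination need not end in confirmation.

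A second argument is that the Eye Disorders Grade 4 row sits under a retinal sub-heading. Its wording extends to other eye disorders. Even if the sub-heading did limit it, Section 6.4.1.3.5 would still conflict with the ocular/visual row.

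Third, Table 3's action column and the title of Section 6.4.1.3.5 are both framed as recommendations, and questions about dose reductions go to the Safety Officer. Withdrawal at the investigator's discretion (Section 7.2) and DSMB review at least twice a year (Section 10.1.6) add protection. These points stand as mitigation: they make unnoticed re-treatment less likely. None of them says which instruction governs.

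It is also true that the counts of combinations and dose levels describe the scope of the conflict, not its frequency, and that no endpoint, sample size or analysis population changes.

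**Conclusion.** The concern holds, as a minor internal contradiction in a safety rule. For a Grade 4 non-retinal eye event that resolves within 14 days, one row permits re-treatment and two provisions require stopping. If the Eye Disorders row is read as retinal only, the count becomes one against one and the contradiction remains. It is confined to the Expansion Cohort and to participants on 125 mg or 100 mg, and its frequency is unknown. Drug is held immediately under every reading, so the only question is whether it may be restarted. The conclusion rests on reading the Grade 3-or-higher label literally, as including Grade 4.

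**What to change.** In Table 3, change the grade label of the other ocular/visual toxicity row to Grade 3 only, and add a Grade 4 line whose action is to discontinue infigratinib. This matches the Eye Disorders block and Section 6.4.1.3.5 whether or not the row is meant for unconfirmed events.

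Deleting the row would also work. The Eye Disorders block already carries the same Grade 3 rule. Any visual toxicity outside that block would fall to the catch-all row (Grade 3: hold, then reduce one level; Grade 4: discontinue), with the table's general limit of 14 days on dose delay still applying. The first option is preferable because it keeps an explicit ocular instruction.

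The cost is one changed label and one added line, or one deleted row, at the next amendment. Visits, data collection and analysis are unaffected.
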